2.0 OBJECTIVES

2.1 Primary Objective

To determine the detection rate, sensitivity, and negative predictive value of SLN biopsy in endometrial cancer patients.

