10.0 MEASUREMENT OF EFFECT

10.1 Sentinel Node Biopsy Evaluation

For the purposes of this study, the success of sentinel node biopsy will be evaluated by the detection rate of the sentinel lymph node for each patient, the sensitivity of the sentinel node to determine the true lymph node status (metastatic disease or not), and the false negative rate. Definitions for these are below. The comparator for these values will be the detection rate, sensitivity, and false negative rate for breast and vulvar cancers, in which sentinel lymph node biopsy is standard practice. In 2005, the American Society of Clinical Oncology stated that for breast cancer, sentinel lymph node detection rate should reach 85% with a false negative rate $\leq 5\%$ [39]. In the most recent randomized trials examining sentinel lymph node biopsy in breast cancer, detection rates ranged from 93-97%. The false negative rates in the SNAC, ALMANAC, and NSABP B-32 trials ranged from 4.7% (ALMANAC) to 9.8% (NSABP B-32) [40, 41, 42]. In vulvar cancer, where sentinel lymph node biopsy has also become more widely accepted, studies similarly report detection rates ranging from 93-98% while false negative rates are approximately 7.7 -8.3% [43,44].

[figure not shown]

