10.1.1 Definitions

Sensitivity, false negative and false negative rate will be limited to those patients in whom a sentinel node is detected.

False negative = a sentinel node that is identified and determined to be negative, however, upon complete lymphadenectomy, a different lymph node is found to be positive

Sensitivity = the number of patients with a positive SLN over those patients with a positive SLN plus those patients with a false negative lymph node

False negative rate = 1-sensitivity or the number of patients with a false negative SLN over the number of patients with a positive SLN plus those with a false negative lymph node

	Our definition	Other definition
FN	H	F+H
FN Rate	$H/D+H$	$F+H/D+F+H$
Sensitivity	$D/D+H$	$D/D+F+H$
NPV	I/E	-

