12.0 STATISTICAL CONSIDERATIONS

Numerical values will be summarized by mean and standard deviation when the data have an approximately normal distribution; otherwise they will be summarized by median and interquartile range. Normality will be evaluated through visual inspection of histograms, boxplots, and normal QQ plots. Analyses specific to each aim are listed below. Secondary multivariable analysis may include logistic regression using metastasis as the dependent variable with type of dy utilized, surgical modality, surgeon, tumor stage, grade and presence of lymphovascular space invasion as independent variables. Significance will be determined by a p-value less than or equal to 0.05 unless otherwise stated.

Specific Aim 1:

Sensitivity, specificity, and negative predictive value of SLN biopsy for detecting metastasis will be estimated and appropriate 95% confidence intervals for each value will be provided.

Specific Aim 2:

Sensitivity, specificity, and negative predictive value of SLN biopsy for detecting metastasis will be compared between surgical modalities using pairwise comparisons for each surgical modality. Comparisons will be performed using two sample tests of proportions based on a normal approximation. Since three such pairwise comparisons are required, significance will be determined by a Bonferonni adjusted significance level of $0.05 / 3 = 0.17$.

Specific Aim 3:

Sensitivity, specificity, and negative predictive value of SLN biopsy for detecting metastasis will be compared between injectants utilized using a two sample test of proportions based on a normal approximation.

Specific Aim 4:

Total operating room time will be estimated as a mean with 95% confidence interval if the data have an approximately normal distribution. Otherwise, the median and a bootstrapped 95% confidence interval for the median will be reported. Similar summaries will be provided for the console time (robotic)/ operating time.

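### Section 12.0 gives detection rate, the first-named primary outcome, no interval and no comparison, so the sensitivity comparisons in Aims 2 and 3 do not count mapping failures; the listed data items do not include the dye injected

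*Combined protocol and SAP*

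**What the plan says.** The primary objective (section 2.1) is "To determine the detection rate, sensitivity, and negative predictive value of SLN biopsy in endometrial cancer patients". Section 10.1 states that "the success of sentinel node biopsy will be evaluated by the detection rate of the sentinel lymph node for each patient", followed by sensitivity and the false negative rate. It then says "The comparator for these values will be the detection rate, sensitivity, and false negative rate for breast and vulvar cancers". For detection it cites a breast cancer guideline, "sentinel lymph node detection rate should reach 85" percent; breast trials in which "detection rates ranged from 93-97" percent; and, for vulvar cancer, "studies similarly report detection rates ranging from 93-98" percent.

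Section 12.0 sets out the analyses aim by aim. For Aim 1, "Sensitivity, specificity, and negative predictive value of SLN biopsy for detecting metastasis will be estimated" with 95% confidence intervals. Aim 2 compares the same three measures between surgical modalities, and Aim 3 compares them between injectants. Both use two-sample tests of proportions. Aim 4 covers operating time. The optional logistic model has metastasis as its outcome and dye type as a covariate.

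Section 10.1.1 adds: "Sensitivity, false negative and false negative rate will be limited to those patients in whom a sentinel node is detected". Its table prints an alternative set of definitions that adds a category F to the sensitivity denominator, but does not adopt it. The key to the letters is not in the text available for this review; it may be in a figure that is not shown.

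Section 6.2 allows isosulfan blue, ICG or both. It lists node counts by dye for each hemipelvis. Neither its variable lists nor the columns of Figure 2 include the dye or dyes injected.

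**The concern.** An outcome that heads the primary objective and has named comparators should have a stated denominator, interval and, where groups are compared, a test. Section 12.0 supplies none of these for detection rate. Specificity, which is not among the objectives, is analysed in Aims 1 to 3.

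The larger problem is in Aims 2 and 3. Sensitivity counts only mapped patients, so a dye or modality that often fails to map loses nothing in that comparison, and no other planned analysis picks up the failures. The study could report two injectants as equivalent on sensitivity when one finds clearly fewer of the node-positive patients.

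Three related defects affect the same comparisons. A patient given both dyes contributes to both groups, which an independent two-sample test does not allow. If a dye has a zero node count, the listed items cannot show whether it failed or was never given. The Aim 2 significance threshold is also misprinted.

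**Working it through.** **The plan's own figures.** Section 3.2 uses a margin of 5%, 95% confidence, a population of 20,000 and a 15% response. With x = 1.96² × 0.15 × 0.85 = 0.490, n = 20,000x / (19,999 × 0.05² + x) = 194.02, or 195 rounded up. The planned 200 is consistent with this. It was sized on the node-positive proportion, not on detection. Aim 2 prints 0.05/3 = 0.17; the quotient is 0.0167.

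**Precision for detection rate.** All 200 patients contribute. Exact (Clopper-Pearson) 95% intervals at rates reported in section 1.3 are:

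| Detected | Rate | 95% CI |
|---|---|---|
| 156/200 | 78% | 71.6–83.5% |
| 178/200 | 89% | 83.8–93.0% |
| 184/200 | 92% | 87.3–95.4% |
| 190/200 | 95% | 91.0–97.6% |

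At 180/200 the lower limit is 84.98%. It first exceeds 85% at 181/200 (90.5%), where it is 85.6%. The planned sample can therefore support a useful statement against the guideline figure.

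Sensitivity rests on far fewer patients. With 9–15% node-positive (section 3.2) and 78–95% mapped, the denominator runs from 200 × 0.09 × 0.78 = 14.0 to 200 × 0.15 × 0.95 = 28.5.

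**Effect of leaving out mapping failures.** Over 78–95% detection, between 200 × 0.22 = 44 and 200 × 0.05 = 10 patients fail to map. Take 93% sensitivity in mapped patients (the section 1.3 meta-analysis) for both dyes, and assume mapping is independent of nodal status. Under section 10.1.1 both dyes have 93% sensitivity. The share of all node-positive patients identified is:

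- dye mapping 78%: 0.78 × 0.93 = 0.7254, or 72.5%
- dye mapping 95%: 0.95 × 0.93 = 0.8835, or 88.4%

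The gap is about 16 percentage points, and the Aim 3 sensitivity test has no difference to find.

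**What a detection comparison could show.** The rates and group sizes here are assumptions; the rates are not specific to the two study dyes. Take 89% versus 95%, two-sided 0.05:

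- One dye each, 100 versus 100: power about 35%.
- Both dyes in all 200, exact McNemar, independent responses: the discordant proportions are 0.95 × 0.11 = 0.1045 and 0.89 × 0.05 = 0.0445, and power is about 53%.
- As above, but with only 1% discordant in the opposite direction (7% and 1%): about 85%.

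For modalities at an assumed 67 versus 67 and a threshold of 0.0167, power is about 13%. For 78% versus 95% it is 69%.

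**Specificity.** If the final sentinel node result is the test, a positive sentinel node is itself nodal metastasis, so no false positive can occur and specificity is 100% by logic. If frozen section (section 6.2) is the test, a false positive is possible, but section 10.1.1 does not define one in its text.

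**The case against.** Section 10.1 does commit to evaluating detection rate per patient and names comparators, and the overall rate can be computed from the node counts in section 6.2. Taken alone, the missing Aim 1 interval is close to a missing detail. The authors also printed an alternative sensitivity definition. If F means node-positive but unmapped, they considered the issue and chose the narrower denominator deliberately. The secondary objective names no metric for comparing dyes or modalities, so no promised detection comparison has been dropped.

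These points stand, but they leave the core intact. A deliberate choice to condition sensitivity on mapping is defensible only if mapping is analysed alongside it, and section 12.0 does not plan that.

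Three stronger readings are tempting and not supported:

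- A reader might infer that the protocol never defines detection rate. A definition may sit in the figure that is not shown.
- A reader might infer that every measure in Aims 2 and 3 excludes unmapped patients. The restriction is explicit only for sensitivity and the false-negative measures; for NPV and specificity it is an inference.
- A reader might infer that the dye given will not be recorded. The documents show only that it is not among the listed items. The database form is not reproduced, and operative records may hold it.

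**Conclusion.** The concern holds in this form: a primary, per-patient outcome with stated comparators has no interval or comparison in section 12.0, and the planned sensitivity comparisons do not see mapping failures. In the illustration this hides a difference of 72.5% versus 88.4% in node-positive patients identified. That figure assumes 93% sensitivity in mapped patients, mapping of 78% and 95%, and independence of mapping from nodal status.

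The two-sample test does not suit patients given both dyes, and 0.17 is an arithmetic slip for 0.0167. The dye ambiguity is confined to zero counts for one dye. Comparisons of detection between dyes or modalities are exploratory: their power depends heavily on assumed rates, splits and discordance, and in the paired case moves from about 53% to 85% on discordance alone. The points should be corrected before analysis, because followed literally the plan can give misleading dye and modality comparisons.

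**What to change.** 1. **Aim 1.** Add per-patient detection rate: patients with at least one sentinel node identified, over all patients injected. Reconcile this with any definition in the figure. Give an exact 95% interval and set it beside all the section 10.1 comparators (85%, 93–97%, 93–98%). If a per-hemipelvis rate is also reported, use a method that allows for two correlated sides per patient.
2. **Aims 2 and 3.** Add detection rate as an exploratory comparison. For injectants, use a paired test such as exact McNemar for patients given both dyes and a two-sample test for patients given one, reported separately. Quote power only as a range over assumed discordance.
3. **Aim 2 threshold.** Replace 0.17 with 0.05/3 = 0.0167.
4. **Data.** Add a field for dye injected: blue, ICG or both.
5. **Specificity.** Drop the comparisons, or state which result is the index test. If it is frozen section, define a false positive; if it is the final sentinel node result, note that specificity is 100% by logic.

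The cost is wording in section 12.0, one data field, a check of operative records for patients already treated, and a few more exploratory comparisons (three between modalities, up to two between injectants). No patients or procedures are added.

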New detection methods and techniques are also currently being investigated, such as the use of fluorescing dye. While further studies are needed to compare these methods to conventional blue dye and isotopes, studies that have utilized ICG in other sites are very promising. ICG is a tricarbo-cyanine dye that fluoresces in the near infrared spectrum when illuminated with 806nm light. The fluorescent light is then captured with a special video camera device that allows the ICG to be displayed in the visible light spectrum. ICG is highly water-soluble and rapidly binds to plasma proteins, qualities that make it useful for assessment of blood flow [21]. Therefore, it has been used surgically to assess patency of grafts in vascular surgery [22], coronary artery bypass grafting [21], transplant surgery and plastic surgery procedures that require flap reconstruction [23]. Because ICG binds to albumin and therefore has a propensity for lymphatic tissue, in the early 2000's, it was first hypothesized that ICG might be a useful injectant for sentinel node identification. In 2005, Kitai et al investigated the use of ICG for SLN biopsy in breast cancer and were the first to propose that the use of ICG could improve both detection rate and negative predictive value of SLN biopsy in breast cancer [24]. This technique has become more popular, particularly for SLN biopsy in breast cancer [25] and melanoma, and recent data suggests that the lymphatic drainage pattern of ICG is identical to that of radioisotope [26]. There are only 2 studies that have utilized ICG for sentinel node detection in endometrial cancer. The first study found that ICG was superior to isosulfan blue for SLN detection and that by using a

combination of ICG and isosulfan blue, a 100% detection rate could be achieved [27]. The other study was a feasibility study for sentinel lymph node biopsy utilizing robotics in both endometrial and cervical cancer patients. This study showed a comparable detection rate to isotope and blue dye in a small sample [28].

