1.4.4 Surgical Modality and Sentinel Lymph Node Biopsy

To our knowledge, thus far, sentinel lymph node biopsy procedures have been performed by laparotomy, conventional laparoscopy, and conventional robotics. Evidence suggests that minimally invasive techniques, including laparoscopy and robotics, should now be the standard of care for endometrial cancer [30], however, at times, open procedures may also be

necessary. Single-port laparoscopy is also now being utilized for endometrial cancer cases [31], yet, to our knowledge, there are no reports of single-port technology utilized for sentinel lymph node biopsy. While there is still limited prospective data on the benefits of single-port techniques, the available data suggests that outcomes for single-port laparoscopy are similar to those of conventional laparoscopy, with the added benefit of improved cosmesis and decreased pain [32].

The most recent advance in single-port technology is the single-port robot, which is now FDA-approved for gynecologic cases [33]. Robotic technology has provided improved optics, improved range of motion, and a shorter learning curve when compared to conventional laparoscopy [34]. A recent study by Escobar et al. compared LESS surgery to conventional LSC and robotic surgery for endometrial cancer and found no difference in outcomes [35]. In a recent study by Rossi et al, the robot was utilized to perform SLN biopsy in both endometrial and cervical cancers. The findings in this study suggest that robotics might have additional advantages specific for SLN biopsy procedure. This study showed a relatively short operating room time (186 min from patient entry into the room until exiting the room), as well as the ability to utilize new and integrated technologies (a fluorescence imager) [28]. These advantages will also translate to single-port robotics as technology develops [31].

1.5. **Rationale**

By performing sentinel lymph node biopsy for endometrial cancer, we may be able to further minimize the risks of lymph node evaluation, while continuing to obtain critical prognostic information for patients. In this study, we examine detection rates, false negative rates, and negative predictive value of SLN biopsy for endometrial cancer in order to further add to the body of evidence on SLN biopsy for endometrial cancer.

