3.2 Number of Subjects

For this study, a sample size of 200 patients will initially be included. This sample size was calculated using the Raosoft sample size calculator online (available at <http://www.raosoft.com/samplesize.html>). A 5% margin of error was used, with a 95% confidence interval, a population size of 20,000 (as suggested), and a 15% response distribution. This 15% response distribution was chosen based on 2 large randomized trials that showed that the rates of positive pelvic lymph nodes in patients with presumed stage I-II disease were 9% and 13% respectively [36, 37]. In order to ensure an adequate sample size a 15% difference was utilized for this calculation.

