8.2 Indocyanine Gree

- Chemical Name:** sodium 4-[2-[(1E,3E,5E,7Z)-7-[1,1-dimethyl-3-(4-sulfonatobutyl)benzo[e]indol-2-ylidene]hepta-1,3,5-trienyl]-1,1-dimethylbenzo[e]indol-3-ium-3-yl]butane-1-sulfonate
- Other Names:** Cardiogreen, Foxgreen, IC-Green
- Classification:** Cyanine Dye
- Mode of Action:** Peak spectral absorption at about 800 nm and therefore visible in the near infrared spectrum. Requires special camera device to visualize. Binds tightly to plasma proteins and therefore has a propensity for lymphatic tissue

Metabolism: removed by the liver and bile

Product description: A fluorescent dye used in medicine as an indicator substance

Solution preparation: available in a powder form and reconstituted in sterile water

Storage requirements: none

Route of administration: cervical

Drug Procurement: indocyanine green must be obtained from commercial sources.

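### Dye and surgical modality are plausibly linked by equipment, yet Aims 2 and 3 test each without holding the other fixed

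*Combined protocol and SAP*

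**What the plan says.** Section 2.2 sets out to compare three modality groups (open, minimally invasive, single-site) and two dyes (isosulfan blue, ICG). In section 12.0, Aim 2 states that sensitivity, specificity and NPV "will be compared between surgical modalities using pairwise comparisons for each surgical modality". Under Aim 3 the same measures are "compared between injectants utilized using a two sample test of proportions based on a normal approximation". Neither aim mentions stratification or adjustment.

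The study is a cohort (section 3.1). Section 6.2 leaves modality to the surgeon and permits either dye or both in the same woman, with no rule for choosing.

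On equipment, section 8.2 says of ICG: "Requires special camera device to visualize". Section 1.4.4 lists a fluorescence imager among the technologies used in a cited robotic study, and adds: "These advantages will also translate to single-port robotics as technology develops". On effect, section 1.4.2 reports: "The first study found that ICG was superior to isosulfan blue for SLN detection".

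One model contains both dye and modality, the logistic regression in section 12.0. It is optional, and its dependent variable is metastasis.

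**The concern.** Blue dye can be seen by eye in any operation, whereas ICG cannot be seen without the camera. If the camera is less available in one modality group, that group will have fewer ICG cases even when surgeons, experience and case mix are the same. A difference between dyes would then show up in Aim 2 as a difference between modalities, and a difference between modalities would show up in Aim 3 as a difference between dyes.

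The optional regression does not resolve this. Modelling which women have metastases, given dye and modality, does not estimate how well the sentinel node finds those metastases.

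At stake is whether either secondary question gets its own answer. The overall estimates for the primary objective are not affected.

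**Working it through.** **The plan's own figure.** Section 3.2 says "a sample size of 200 patients will initially be included", from a calculator with a 5% margin, "with a 95% confidence interval, a population size of 20,000 (as suggested), and a 15% response distribution". With x = 1.96² × 0.15 × 0.85 = 0.4898, n = 20,000 × 0.4898 / (19,999 × 0.05² + 0.4898) = 194.0, so 195. The stated 200 reproduces. It is a precision calculation for one proportion and sizes neither Aim 2 nor Aim 3.

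**Bias formula.** Suppose modality has no effect and dye has the same effect in every modality. Then:

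apparent modality difference = (rate with ICG − rate with blue) × (ICG share in group A − ICG share in group B).

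The converse holds for Aim 3: with no dye effect, the apparent dye difference between two modality groups is the modality effect times the difference in modality mix between dyes.

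**Inputs.** ICG share by modality is not in the documents, so a range is assumed. Dye-specific sensitivities are not given either. The values 84% (blue) and 93% (ICG) are assumptions. Both numbers appear in section 1.3, but the first comes from an isotope-plus-blue study and the second is a pooled meta-analysis figure.

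| ICG share, A vs B | Apparent sensitivity difference |
|---|---|
| 50% vs 50% | 0.09 × 0 = 0 points |
| 60% vs 40% | 0.09 × 0.2 = 1.8 points |
| 60% vs 20% | 0.09 × 0.4 = 3.6 points |
| 80% vs 20% | 0.09 × 0.6 = 5.4 points |
| 80% vs 0% | 0.09 × 0.8 = 7.2 points |
| 100% vs 0% | 0.09 × 1.0 = 9.0 points |

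**NPV, same assumptions.** With no false positives, NPV = (1 − π)/[(1 − π) + π(1 − sensitivity)], where π is the node-positive proportion. At 80% versus 0% ICG, group A has sensitivity 0.8 × 0.93 + 0.2 × 0.84 = 0.912 and group B has 0.84.
- π = 0.09: 0.91/0.91792 = 99.1% versus 0.91/0.9244 = 98.4%, a gap of 0.7 points.
- π = 0.15: 0.85/0.8632 = 98.5% versus 0.85/0.874 = 97.3%, a gap of 1.2 points.

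**Node-positive women.** Section 3.2 gives positive-node rates that "were 9% and 13% respectively" and plans on 15%. So 200 × 0.09 = 18 to 200 × 0.15 = 30 women. Section 10.1.1 limits sensitivity to women with a detected node. At 78% to 92% detection (section 1.3) that leaves 18 × 0.78 = 14 to 30 × 0.92 = 28. Across nine cells (three modalities by blue only, ICG only, both), even the full 18 to 30 average 2.0 to 3.3 per cell.

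**False significance on sensitivity.** Take 100 versus 50 women, ICG in 80% versus 0%, and no modality effect. Node-positive numbers are about 9 versus 5 (at 9%) to 15 versus 8 (at 15%). Exact enumeration of the pooled z-test with true values 91.2% and 84% gives rejection of about 8–11% at 0.05 and 1.5–4% at 0.0167. With 84% in both groups it is 4–5% and 0.8–1.6%. The level used here is 0.05/3 = 0.0167. Section 12.0 prints it as 0.17, a separate slip.

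**The case against.** The strongest reply is that the link between dye and modality is inferred, and much of that stands. No rule in the protocol ties ICG to one modality. Section 6.1 places ICG in the operating rooms of all named campuses. Section 1.4.2 describes the camera generically and cites ICG use in vascular, coronary, transplant and plastic surgery. The remark in section 1.4.4 is background on a cited study. It implies something about single-port robotics and nothing about open surgery or conventional laparoscopy.

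A reader might infer that dye and modality are fully aliased, with ICG confined to the multi-port robot. The documents do not support that: blue dye can be used in every modality, ICG is not restricted, and section 2.2 has no multi-port-robot group.

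A reader might also expect frequent false-positive modality claims. For detection, assuming 80% with blue and 95% with ICG, 80% versus 0% ICG, and 100 versus 50 women, the z-test compares 92% with 80% and rejects 57% of the time at 0.05 and 40% at 0.0167. But Aims 2 and 3 do not test detection, and the weaker link (60% versus 20%) gives only 19% and 10%. The ICG superiority reported in section 1.4.2 also concerns detection. No blue-versus-ICG contrast in sensitivity is given.

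Finally, these are secondary comparisons in a cohort, and section 6.2.1-type detail aside, the data listed after section 6.2 already count sentinel nodes by each dye. That helps only in part. A zero count for ICG does not show whether ICG failed or was never injected, and imager use is not listed.

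**Conclusion.** The point holds as potential confounding of unknown size. Both factors are non-randomised, the protocol itself gives an equipment reason for them to be linked, and each is tested marginally with no usable model to separate them. Bias arises only if ICG use differs by modality and the dye (or modality) has an effect.

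Under the assumed 84% and 93%, a modality contrast in sensitivity is off by 0 points at equal ICG shares, about 4 at 60% versus 20%, and about 7 at 80% versus 0%. The matching NPV bias at 80% versus 0% is about 1 point. With so few node-positive women, the main harm for sensitivity is a misleading estimate more than a false significant result. The documents establish neither complete aliasing nor a high false-positive rate on the planned measures.

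The change is worth making because it is cheap and shows whether the problem is large or absent.

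**What to change.** In section 12.0, Aims 2 and 3:

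1. Report the modality-by-dye table (blue only, ICG only, both) before any comparison.
2. For NPV, and for detection if it is compared, compare modalities within dye group and dyes within modality, combined by an exact stratified estimate.
3. In women given both dyes, compare dyes by a paired within-patient analysis (McNemar type). This holds modality fixed. The independent two-sample test does not fit these women.
4. Report sensitivity contrasts as descriptive, with exact intervals, given about 18–30 node-positive women in all.
5. Where a modality-by-dye cell is empty, state that the contrast cannot separate dye from modality, and label any marginal result as unadjusted.

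Record for each patient the dye(s) given and whether a fluorescence imager was used, for example as two fields on the Figure 2 sheet.

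The cost is some analysis-plan wording and two data fields. The downside is wider intervals and some contrasts declared not estimable.
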